## 4.0 STUDY DESIGN

# 4.1 General Design

• This phase I clinical trial will use a Simon two-stage design. In the first stage, 6 patients will be enrolled, if the patients in the study do not meet the termination criteria then the study will extend to a second stage and we will enroll a maximum of 20 patients. Patients will be treated with skindirected radiotherapy, using a total prescription dose of 7.5 Gy in five fractions of 1.5 Gy over one week. Neither patient nor insurance will be billed for the radiotherapy procedures. If any subject experiences Grade > 3 toxicities, the study will be stopped and the IRB will be informed immediately so the study can be reevaluated.

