#### Interim Analysis.

Once the first 6 patients are recruited, the study recruitment will be temporarily suspended and the patients will be followed for 3 months to monitor any toxicity issues. At the end of 3 months follow-up of the 6 patients, the results will be sent to the DSMB for further evaluation. The trial will be terminated if grade 3 or more toxicity is observed in more than 2 patients or at least one showing grade 4 level toxicity. Otherwise, upon approval from the DSMB, the second phase of recruiting will be initiated.

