#### 5.0 STATISTICAL CONSIDERATIONS

A maximum of 20 patients will be enrolled into the study. The accrual rate is expected to be 1-2 patients per month based on the volume of patients with stage 2-3 HS treated within the Montefiore Hidradenitis Suppurativa Treatment Center. An early stopping rule for safety will be implemented as follows based on Simon's optimal two-stage design. After the first 6 patients have been enrolled, accrual will be temporarily suspended while these patients are monitored for occurrence of treatment-related grade ≥ 3 toxicity for 3 months. At the end of 3

months, results will be sent to the DSMB for further evaluation. The trial will be terminated early if more than 1 patient experiences grade  $\geq$  3 treatment related toxicity or any patient experiences grade 4 toxicity. Otherwise, upon approval from the DSMB, the second phase of recruiting will be initiated. If 1 or fewer grade  $\geq$  3 toxicities and 0 grade 4 toxicities are observed, the trial will continue until a total of 20 patients have been evaluated. At the end of the trial, the treatment will be considered safe and worthy of further study if no more than 3 patients experience grade  $\geq$  3 treatment related toxicity and none experience grade 4 treatment related toxicity.

The target Grade  $\geq$  3 toxicity rates is no more than 10%, and a toxicity rate greater than 30% is considered clinically unacceptable. The design specified above has the following operating characteristics. The probability of accepting the treatment for further study if the toxicity rate is unacceptably high (> 30%) is at most 10%. In contrast, there is an 80% probability of accepting the treatment for further study if the toxicity rate is less than 10%. In addition, if 0 out of 20 patients experience Grade 4 toxicity at the end of the study, we will be able to conclude with 95% confidence that the true Grade 4 toxicity rate is not greater than 17%.

The proportion of patients who have treatment-related toxicity will be computed, along with exact 95% confidence intervals. Since the study is a phase I trial, we will NOT do any hypothesis testing or models, The study will present the descriptive summary statistics for each outcomes. Biomarker levels measured at different time points and other continuous variables will be summarized by computing means, medians, standard deviations and ranges.

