# 8.0 Data Safety and Monitoring Boards

A Data Safety Monitoring Committee is being convened by [name]. They will have the responsibility for ensuring data and safety monitoring along with the PI who is ultimately responsible for the ongoing monitoring and safety of clinical protocols. The primary functions of this DSMC are as follows:

- To review and ensure protocol compliance with dose escalation in phase I trials
- 2. To review/assure protocol compliance for all trials that have two-stage phase II designs,
- Reviewing all internal and external serious adverse reports, investigator alerts, action letters, and other safety reports for trials being performed at AECC-affiliated institutions and;
- 4. To implement and to determine the adequacy of DSM plans of all approved protocols.

The committee will meet quarterly or more frequently as needed. This committee lead by [name] will review serious (grade 3 or higher) adverse events from this study. In the event that the DSMC decides that a revision is warranted, the committee will immediately notify the principal investigator of this study. The DSMC has the authority to close trials to patient accrual should the risk to patients be excessive or outweigh the potential benefits of the study. All study

suspensions and closures will be forwarded to the IRB/CCI and study sponsor from the DSMC.

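### Accrual can run on to 20 after a fourth Grade ≥3 toxicity has already decided the safety verdict: a cheap curtailment rule for stage 2 would prevent this

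*Combined protocol and SAP*

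**What the plan says.** Section 5.0 sets the rule out in this way: "An early stopping rule for safety will be implemented as follows based on Simon's optimal two-stage design". Six patients are enrolled and watched for 3 months. The trial ends there if more than 1 has treatment-related Grade ≥3 toxicity or any has Grade 4. Otherwise, with committee approval, "the trial will continue until a total of 20 patients have been evaluated". The final criterion is then applied: "At the end of the trial, the treatment will be considered safe and worthy of further study if no more than 3 patients" have treatment-related Grade ≥3 toxicity and none has Grade 4.

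Three other provisions bear on stopping:

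- **Section 4.1, General Design:** "If any subject experiences Grade > 3 toxicities, the study will be stopped". As printed, this does not cover Grade 3.
- **Section 4.1, Interim Analysis:** "The trial will be terminated if grade 3 or more toxicity is observed in more than 2 patients". This belongs to the 6-patient look, and its limit differs from the one in Section 5.0.
- **Section 8.0:** the committee reviews events of Grade 3 or higher. "The committee will meet quarterly or more frequently as needed", and "The DSMC has the authority to close trials to patient accrual should the risk to patients be excessive". No count is attached.

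**The concern.** The final verdict depends on a count that can only rise. When a fourth patient is affected, whether that is patient 9 or patient 20, the treatment has failed the plan's own safety criterion. Section 5.0 nevertheless directs the trial on to 20, and none of the other provisions closes accrual automatically on Grade 3 events in stage 2.

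A two-stage design of this kind normally has no boundary inside stage 2, so its absence is not a departure from the method. Here, though, the counted event is harm. The disease is benign, safety is the primary objective, and Section 10.0 rates the protocol as more than minimal risk. Patients enrolled after the fourth event would be irradiated when their results can no longer alter the accept/reject decision.

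**Working it through.** **Inputs, all from Section 5.0.** Stage 1 has 6 patients and continues if at most 1 is affected. The total is 20, so stage 2 has 14, and the treatment is accepted if at most 3 of 20 are affected. The reference rates are 10% (target) and 30% (unacceptable). Accrual is 1–2 patients per month and the toxicity window is 3 months. Grade 4 is not modelled because the plan gives no Grade 4 rate.

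**Step 1: reproduce the plan's figures.** Let p be the true Grade ≥3 rate, X₁ ~ Bin(6, p) and Y ~ Bin(14, p).

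P(accept) = P(X₁=0)·P(Y≤3) + P(X₁=1)·P(Y≤2)

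- p = 0.10: 0.5314 × 0.9559 + 0.3543 × 0.8416 = 0.8062 (plan: 80%)
- p = 0.30: 0.1176 × 0.3552 + 0.3025 × 0.1608 = 0.0904 (plan: at most 10%)

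The stated operating characteristics hold. A search for Simon's optimal design at these rates, with error 0.10 and power 0.80, returns this same design.

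**Step 2: how often the verdict is settled before patient 20.** A trial that enters stage 2 either ends with at most 3 affected patients or reaches a fourth. Therefore

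P(pass stage 1, then fourth affected) = P(X₁≤1) − P(accept)

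At p = 0.30 this is 0.4202 − 0.0904 = 0.330 (0.3297 before rounding). That is 78.5% of the trials that enter stage 2.

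**Step 3: when it happens and who is left.** If stage 1 has x affected patients, the fourth affected patient is stage 2 patient k with probability C(k−1, 3−x)·p^(4−x)·(1−p)^(k−4+x), leaving 14 − k still to enrol. With a reporting lag of L patients, the number left is max(0, 14 − k − L). The plan's rates give L = 3 × 1 = 3 to 3 × 2 = 6 for a full three-month lag.

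| True rate | Enter stage 2 | Then a fourth affected (all trials) | Mean left, given a fourth: L = 0 / 3 / 6 | Mean left, all trials: L = 0 / 3 / 6 |
|---|---|---|---|---|
| 10% | 88.6% | 8.0% | 3.18 / 1.17 / 0.27 | 0.25 / 0.09 / 0.02 |
| 20% | 65.5% | 29.6% | 4.09 / 1.78 / 0.50 | 1.21 / 0.53 / 0.15 |
| 30% | 42.0% | 33.0% | 5.24 / 2.65 / 0.89 | 1.73 / 0.88 / 0.29 |
| 40% | 23.3% | 22.0% | 6.56 / 3.74 / 1.48 | 1.44 / 0.82 / 0.33 |

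At 30% the median position of the fourth affected patient, given that one occurs, is patient 15. The earliest possible is patient 9, with 11 still to enrol.

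**Step 4: effect of curtailing.** Closing accrual at the fourth affected patient affects only trials that are already certain to be rejected. P(accept) stays at 0.8062 and 0.0904.

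**Step 5: price in precision.** Exact (Clopper–Pearson) 95% intervals for the toxicity proportion are 4/9: 13.7–78.8%; 4/15: 7.8–55.1%; 4/20: 5.7–43.7%. These treat the denominators as fixed.

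**The case against.** The plan does what it claims. A standard Simon design has no stage 2 boundary, and the stated limits are met, so this can be called a reviewer's preference. The benefit is also modest where the investigators expect to be: 0.25 patients per trial at the 10% target with no lag, and 0.03 at an assumed 5%. Even at 30%, given a fourth event, the rule spares nobody in 31% of trials with a 3-patient lag and in 63% with a 6-patient lag. All of this stands, and it is why the point is put as an improvement. The full lag is the slow extreme, however. The study calendar in Section 4.2 assesses adverse events at weeks 1, 5, 9 and 13, so many would be known sooner.

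Oversight is not absent. The committee sees every event of Grade 3 or higher, the principal investigator is ultimately responsible for safety (Section 8.0), may act on an immediate hazard (Section 6.2), and events go to the IRB (Section 9.2). That is fair. But each route rests on judgement, and none is tied to the count that decides the verdict. With quarterly meetings as the minimum, 3 to 6 patients can enrol between scheduled meetings.

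If the General Design rule in Section 4.1 was meant to include Grade 3, the proposal would be redundant. That reading would conflict with the allowances for Grade 3 events in the Interim Analysis text and in Section 5.0, so it cannot be assumed.

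Stopping on an affected patient also makes the observed proportion tend to read high, and fixed-denominator intervals do not correct for this. That stands as a real, small cost.

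**Conclusion.** The point holds as an inexpensive improvement to a design that is otherwise sound on its own terms. Section 5.0 gives no numeric Grade 3 boundary for patients 7 to 20, so accrual can continue after the final criterion has failed unless someone uses discretion to stop it. At a true 30% rate this situation arises in a third of all trials. It leaves on average 5.2 patients still to be enrolled with immediate knowledge of toxicity, or 2.7 to 0.9 with a three-month lag. At the 10% target it arises in 8.0% of trials.

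These figures assume independent patients with a common toxicity rate, the Section 5.0 stage 1 limit (at most 1 of 6), and the Grade > 3 rule in Section 4.1 read as printed. The lag range assumes the plan's accrual rate of 1–2 per month.

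**What to change.** Add two sentences to Section 5.0, for example:

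> Stage 2 accrual closes once the final criterion of this section can no longer be met, including when a fourth patient (stages 1 and 2 combined) has treatment-related Grade ≥3 toxicity. The treatment is then not considered safe under that criterion.

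This applies only the plan's existing final criterion, including its Grade 4 limb. It sets no new threshold and leaves stage 1 alone.

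**Cost.** Maximum sample size and acceptance probabilities are unchanged. In trials that have already failed on safety there would be fewer patients for the descriptive secondary endpoints, a wider exact interval for the toxicity proportion (about 8–55% at 4/15 against 6–44% at 4/20), and a proportion that tends to read high. The report of a curtailed trial should say so.

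**Separate action.** The stopping statements in Section 4.1 (General Design and Interim Analysis) and Section 5.0 disagree and must be reconciled by the sponsor. The choice has consequences: with the Interim Analysis limit of 2 in stage 1, acceptance at 30% toxicity would be 10.6%, above the 10% that Section 5.0 states. If the reconciled text stops the study on any Grade 3 event, the added sentences become unnecessary.

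### The zero-tolerance clauses for severe toxicity say grade 4 rather than grade 4 or higher, so the rule for declaring the treatment safe does not name Grade 5

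*Combined protocol and SAP*

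**What the plan says.** Section 5.0 uses a two-stage rule on 6 and then 20 patients. Each decision has two parts: a limit on the number of patients with treatment-related toxicity of grade 3 or higher, and zero tolerance for a more severe grade. The zero-tolerance part appears four times:

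- Interim stop, Section 5.0: terminate if "any patient experiences grade 4 toxicity".
- Continuation, Section 5.0: with at most one toxicity of grade 3 or higher and "0 grade 4 toxicities are observed, the trial will continue until a total of 20 patients have been evaluated".
- Final conclusion, Section 5.0: "the treatment will be considered safe and worthy of further study if no more than 3 patients experience grade" 3 or higher, and "none experience grade 4 treatment related toxicity".
- Interim Analysis paragraph, Section 4.1: terminate on "at least one showing grade 4 level toxicity".

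Section 5.0 also gives a zero-event bound in the same terms. With 0 of 20 patients affected, the "true Grade 4 toxicity rate is not greater than 17" percent.

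Two other provisions bear on the point. General Design in Section 4.1 has a stopping rule that begins "If any subject experiences Grade > 3 toxicities"; the study then stops and goes to the IRB for re-evaluation. Section 8.0 says the monitoring committee "will review serious (grade 3 or higher) adverse events" and gives it authority to close accrual.

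**The concern.** In Section 5.0 the grade 3 threshold carries a ≥ sign in the same sentences where grade 4 stands bare. The Interim Analysis paragraph likewise makes grade 3 open-ended but not grade 4. A reader who takes the notation at face value will read grade 4 as that grade alone. Appendix B shows that Grade 5 is a separate level of the scale, with death entered for bullous dermatitis and skin induration.

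On that reading the rule is not monotone in severity: the worse event can give the better verdict. Safety is the primary objective and the primary endpoint, and the final clause is the only stated rule for declaring it. A prespecified safety verdict should not need the reader to infer that a death counts at least as heavily as a Grade 4 event.

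**Working it through.** **1. Inputs (Section 5.0).** Stage 1 has 6 patients and continues with at most 1 toxicity of grade ≥ 3. The total is 20 patients, and the treatment is accepted with at most 3. Target toxicity rate 10%, unacceptable rate 30%. Stated acceptance probabilities: 80% at 10%, and at most 10% at 30%. Stated bound for 0 of 20: 17%.

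**2. Reproducing the stated operating characteristics.** With p the rate of grade ≥ 3 toxicity,

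P(accept) = P(X₁=0)·P(Y≤3) + P(X₁=1)·P(Y≤2), where X₁ ~ Bin(6, p) and Y ~ Bin(14, p).

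- p = 0.10: 0.5314 × 0.9559 + 0.3543 × 0.8416 = 0.5080 + 0.2982 = **0.806** (stated 80%).
- p = 0.30: 0.1176 × 0.3552 + 0.3025 × 0.1608 = 0.0418 + 0.0487 = **0.090** (stated at most 10%).

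Both agree with the plan. The formula counts grade ≥ 3 only. It contains no term for the zero-tolerance clause, so it gives the same figures under either wording.

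**3. Reproducing the zero-event bound.** The exact two-sided 95% upper limit for 0 of 20 is 1 − 0.025^(1/20) = **0.168**, which agrees with the stated 17%. It depends only on 0 events in 20 patients, so it holds equally for grade ≥ 4.

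**4. Applying the final rule literally to 20 patients.** Each row assumes no other event of grade ≥ 3.

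| Single treatment-related event | Count of grade ≥ 3 (limit 3) | Count of Grade 4 (limit 0) | Verdict as written | Verdict with grade ≥ 4 |
|---|---|---|---|---|
| Grade 3 | 1 | 0 | accepted | accepted |
| Grade 4 | 1 | 1 | rejected | rejected |
| Grade 5 | 1 | 0 | **accepted** | rejected |

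The last row is the defect. The same pattern holds at the interim, where one Grade 5 event among the first 6 gives a count of 1 against a limit of 1, with no Grade 4.

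**5. Which clauses reach Grade 5.** The general stopping rule in Section 4.1 does, because above 3 means 4 or 5. It governs conduct and says nothing about the conclusion. The four clauses listed above do not name Grade 5. It enters them only as one more event of grade ≥ 3.

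**6. Size if such events occurred (illustration only).** The documents give no Grade 4 or Grade 5 rate. Assume a Grade 4 rate of 0 and a Grade 5 rate q inside p = 0.10. Under the grade ≥ 4 wording, any Grade 5 event rejects. The formula in step 2 then applies with each toxicity term using p − q, and the no-toxicity probability 1 − p unchanged. P(accept) falls from 0.806 under the literal wording to 0.688 at q = 1% and 0.341 at q = 5%. Nothing in the plan suggests rates of that order.

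**The case against.** The strongest reply is that this is an editorial slip that other provisions largely cover. Any event above grade 3 stops the study under Section 4.1, stage 2 needs DSMB approval, and the committee in Section 8.0 reviews events of grade 3 or higher and can close accrual. A trial with a death would have been halted long before anyone applied the final sentence. That stands for the accrual period. It does not settle the final verdict, because none of these provisions defines it. For an event after the last patient is enrolled there is little left to stop, and the final rule is what remains.

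Second, Grade 5 is not missing from the rule altogether. It counts toward the limits of 1 of 6 and 3 of 20, and under Section 4.3 it is a primary-endpoint event. That is correct. The gap is confined to the zero-tolerance part.

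Third, a patient who died might first have had a recorded Grade 4 event and so would fail the rule as written. That is possible, since the plan does not say whether only the worst grade per patient is scored. The result in the table needs a Grade 5 event with no Grade 4 recorded for that patient, or scoring by worst grade. An acceptance rule should not turn on that detail.

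Fourth, the > sign in Section 4.1 could be a ≥ that lost its underline in PDF conversion. If so, it is a weaker guide to the intended threshold. The case for grade ≥ 4 in the other clauses does not depend on it.

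**Conclusion.** The concern holds, as a minor point. Four clauses set zero tolerance at grade 4 alone, and the only rule for declaring the treatment safe would, read literally, reject on one Grade 4 event and accept on one treatment-related death. The authors very likely intended grade 4 or higher. Every figure in Section 5.0 that was checked (80%, at most 10%, 17%) reproduces and is unaffected.

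The practical weight is small. A treatment-related death is remote at 7.5 Gy in five fractions to a single region, and the safeguards during accrual are real. This is a clarification of a decision rule and is unlikely to change the trial's result. The conclusion rests on a literal reading of the grade notation and on a Grade 5 event with no separately counted Grade 4 event.

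**What to change.** Write grade ≥ 4 in place of grade 4 in the interim-stop, continuation and final-acceptance clauses of Section 5.0, and in the Interim Analysis paragraph of Section 4.1. This matches the general stopping rule in Section 4.1 as printed. Optionally restate the zero-event bound for grade ≥ 4, keeping 17%.

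The cost is a wording change in four clauses. Sample size, the limits of 1 of 6 and 3 of 20, and the stated operating characteristics stay as they are.

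The same amendment should settle a separate mismatch that this edit leaves in place. The Interim Analysis paragraph stops at more than 2 patients with grade 3 or higher, while Section 5.0 stops at more than 1. Under the looser limit the acceptance probabilities would be 0.864 at 10% and 0.106 at 30%, the latter above the stated maximum of 10%. The stated figures therefore belong to the Section 5.0 limit.

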As reviewed in above case report, a center in Germany treated 231 HS patients over 20 years who failed other treatment options. These patients received multiple fraction schedules with multiple fraction sizes (0.5 Gy - 1.5 Gy per fraction up to a total dose of 3.0 Gy to 8.0 Gy in one series). Chronic

recurrences were treated with 2 or more series with a total dose of greater than 10.0 Gy. No acute side effects were observed in this study. Complete symptomatic relief was documented in 38% (89/231) patients by the end of therapy and 40% (92 / 231) of patients reported an overall improvement in symptomatology. Only two patients had no response.

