# 4.4.2 Target Volumes and Treatment Planning

While patients with hidradenitis suppurativa may have multiple sites of symptomatic disease, subjects on this protocol will only receive radiotherapy directed at one region. This will generally be the region that is most bothersome to the patient.

Computed tomography will be the primary image platform for targeting and treatment planning. Radio-opaque markers may be placed on the patient at the time of simulation to aid with target delineation. Target volumes will be drawn on simulation CT imaging, using appropriate window levels. The general intent will be to include any grossly abnormal areas, based on clinical examination and CT findings, in the GTV. In selected cases of extensive disease, the GTV may be limited to the most problematic area of disease.

The GTV will be expanded to form a PTV. PTV expansions will generally be 10 mm in all directions but may be between 5 and 15 mm depending on the perceived setup uncertainty in each individual case. Nonuniform expansions are permitted, at the discretion of the treating physicians.

Treatment planning will be performed using standard software packages utilized in the Department of Radiation Oncology. Treatment may be delivered using external beam radiotherapy (EBRT) with either photons or electrons, or with high dose rate (HDR) brachytherapy, at the discretion of the treating physicians. The modality that is expected to provide the most complete coverage of the target volumes while minimizing irradiation of uninvolved tissues will generally be selected. The prescription isodose surface should encompass at least 95% of the PTV, and the minimum PTV dose must not fall below 90% of the prescription dose.

Patients in this study will receive a total radiotherapy dose of **7.5 Gy in five daily fractions of 1.5 Gy**.

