### 10.0 RISKS/BENEFITS

- Anticipated risks (medical, social, psychological, and/or legal)
  - This protocol is considered greater than minimal risk, due to radiation exposure and the skin biopsy procedure.
  - The initial risk of radiotherapy is temporary discomfort and inconvenience during the treatment period.
  - This dose of radiotherapy may cause temporary hair loss at the treatment site for a few months.
  - The risk of acute or chronic radiation-induced dermatitis is thought to be very low with the dose of radiotherapy being employed in this study.
  - A risk of low-intermediate dose radiation is Radiation Induced Cancer (RIC) such as skin cancer (BCC, SCC, melanoma)[2]. In patients treated for benign disease with intermediate dose radiotherapy (Range 3-50 Gy, mean approximately 20Gy), normal tissue side effects are rare or minimal. RIC risk is normally very small in adults (<1%) and decreases with increasing age.

  - o Blood draw may cause discomfort, pain, and bruising.
  - Risks from skin biopsy may include temporary pain during the procedure, a small chance of infection, and the possibility that biopsy leaves a small scar.
  - A psychological risk is that the treatment will not have any clinical improvement.
  - o Breach of confidentiality is a possible risk if data is lost or stolen.
- How anticipated risks will be minimized
  - To minimize RIC risks- careful body positioning during radiotherapy and shielding of tissues outside of the intended treatment field will be

- employed in a customized fashion for each patient. In most cases, treatment with superficial forms of radiotherapy (electrons or surface brachytherapy) will be employed to minimize the volume of tissue irradiatied.
- Lab tests and skin biopsy will be performed carefully, using standard safety measures.
- o Confidentiality will be maintained as described in Section 7.1.
- Potential benefits
  - Potential benefits include disease improvement and potential remission, along with improved quality of life

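### Section 5.0 attributes its 80% and 10% acceptance probabilities to the full decision rule, but they cover only the Grade ≥3 boundaries and leave out the zero-Grade-4 condition (minor correction)

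*Combined protocol and SAP*

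**What the plan says.** Section 5.0 sets a two-stage rule. After 6 patients the trial stops if more than 1 has treatment-related Grade ≥3 toxicity or if any has Grade 4. After 20, the treatment is accepted if no more than 3 have treatment-related Grade ≥3 toxicity and "none experience grade 4 treatment related toxicity". The target Grade ≥3 rate is at most 10%, and a rate above 30% is unacceptable.

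The next paragraph states: "The design specified above has the following operating characteristics". It gives at most 10% acceptance above a 30% rate and, on the favourable side, "there is an 80% probability of accepting the treatment for further study if the toxicity rate is less than 10" per cent. Grade 4 then gets its own sentence, a confidence bound of 17% if 0 of 20 patients are affected. The plan gives no assumed Grade 4 rate.

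Section 4.1 states the stopping rules differently. Its Interim Analysis paragraph terminates if "grade 3 or more toxicity is observed in more than 2 patients or at least one showing grade 4 level toxicity". Its General Design paragraph adds: "If any subject experiences Grade > 3 toxicities, the study will be stopped".

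**The concern.** The probabilities are offered for the design as specified, and that design has two acceptance conditions: a count of Grade ≥3 patients and the absence of Grade 4. A second necessary condition can only lower acceptance at a given Grade ≥3 rate, and it does so strictly whenever Grade 4 has a non-zero rate. If 80% comes from the first condition alone, a reader who takes it as the chance that an acceptably safe treatment goes forward under the written rule has a figure for a looser rule.

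The stage 1 boundary raises a further question, because both probabilities depend on which of the stated versions applies.

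**Working it through.** **Inputs.** From Section 5.0: 6 patients at stage 1 and 20 in total, continue with at most 1 toxic patient, accept with at most 3, and Grade ≥3 rates p of 10% and 30%. From the Interim Analysis paragraph: continue with at most 2 of 6. Assumed, because the documents give no figure: a Grade 4 (or higher) rate g of 0 to 1%. Grade 4 is treated as a subset of treatment-related Grade ≥3 events, and each toxic patient reaches Grade 4 independently with probability q = g/p.

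**Formula.** The probability of ending with k toxic patients inside the boundaries is c_k · p^k · (1−p)^(20−k), where c_k counts the permitted arrangements. With at most 1 at stage 1:
- c0 = 1 and c1 = 20
- c2 = C(20,2) − C(6,2) = 190 − 15 = 175
- c3 = C(14,3) + 6·C(14,2) = 364 + 546 = 910

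The full rule multiplies each term by (1−q)^k.

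**Step 1: reproduce the plan's figures (q = 0).**
- p = 10%: 0.12158 + 0.27017 + 0.26267 + 0.15176 = 0.806.
- p = 30%: 0.00080 + 0.00684 + 0.02565 + 0.05716 = 0.090.

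These match the stated 80% and at most 10%. A search for Simon's optimal design (non-toxicity 70% against 90%, α = 0.10, β = 0.20) returns the same boundaries: continue with at least 5 of 6 non-toxic, accept with at least 17 of 20. The stated pair is therefore the standard Simon result with no Grade 4 condition.

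**Step 2: add the zero-Grade-4 condition at p = 10%.**
- g = 0.05% (q = 0.005): 0.12158 + 0.26882 + 0.26005 + 0.14950 = 0.7999, the point where 80% is crossed.
- g = 0.5% (q = 0.05): 0.12158 + 0.25666 + 0.23706 + 0.13012 = 0.745.
- g = 1% (q = 0.10): 0.12158 + 0.24315 + 0.21276 + 0.11063 = 0.688.

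Acceptance under the full rule, Section 5.0 boundaries:

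| Grade ≥3 rate | g = 0 | g = 0.1% | g = 0.5% | g = 1% | g at which acceptance is 80% |
|---|---|---|---|---|---|
| 10% | 80.6% | 79.4% | 74.5% | 68.8% | 0.05% |
| 8% | 87.9% | 86.5% | 80.9% | 74.3% | 0.565% |
| 5% | 95.7% | 94.0% | 87.4% | 79.6% | 0.973% |
| 3% | 98.6% | 96.7% | 89.6% | 81.3% | 1.081% |

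At p = 30%, acceptance is 9.0% with q = 0 and 7.9% with q = 0.05, so the 10% limit holds.

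**Step 3: the Interim Analysis boundary.** That paragraph gives no final boundary, so Section 5.0's limit of 3 in 20 is borrowed. Now c2 = 190 and c3 = 910 + C(6,2)·14 = 910 + 210 = 1120.
- p = 10%, q = 0: 0.12158 + 0.27017 + 0.28518 + 0.18678 = 0.864.
- p = 30%, q = 0: 0.00080 + 0.00684 + 0.02785 + 0.07035 = 0.106, above the stated 10%. It returns to 10% only when about 2.2% of toxic patients reach Grade 4.

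The Section 4.1 stop for any event above Grade 3 gives the same acceptance probability as the zero-Grade-4 condition, provided a stopped study counts as not accepted.

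**The case against.** The best defence is that the paragraph is about the Grade ≥3 rate throughout. It opens with the target for that rate, states both probabilities as functions of it, names Simon's design, and turns to Grade 4 only afterwards. This explains where the 80% comes from. It does not restrict it: the lead-in refers to the whole design, and the later sentence is a confidence bound that says nothing about what the 80% leaves out.

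A second defence is that Grade 4 is improbable here, and the documents do point that way:
- Section 2.3 says of a series of 231 HS patients: "No acute side effects were observed in this study". With 0 of 231, the exact one-sided 95% upper bound is 1 − 0.05^(1/231) = 1.3% for acute effects of any grade, though the report is second-hand and covers acute effects only.
- Section 4.4.2 states that "subjects on this protocol will only receive radiotherapy directed at one region".
- Section 10.0 says the risk of "radiation-induced dermatitis is thought to be very low".
- In Appendix B, five of the eight listed items have no Grade 4 entry.

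This stands. It supports the low end of the assumed range and keeps the point minor, but the missing qualifier still has to be written.

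Three stronger readings are tempting and not supported:
- *The 80% is miscalculated.* It is not; it is right for the Grade ≥3 boundaries.
- *Acceptance is below 80% whenever Grade 4 can occur.* It is below the boundary-only value at the same rate, which is a different statement. At a 5% rate with 0.1% Grade 4 it is 94.0%.
- *Patient protection is weakened.* Under the Section 5.0 boundaries the extra condition lowers false acceptance, and rejecting after a Grade 4 event is what the rule intends.

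**Conclusion.** The point holds as a minor correction. Section 5.0 attributes to the full rule two probabilities that belong to the Grade ≥3 boundaries alone. That the full rule accepts less often at the same Grade ≥3 rate needs no assumption beyond a non-zero Grade 4 rate; only the size does. On the assumed range, the loss at a 10% Grade ≥3 rate runs from 1.2 points (80.6 − 79.4) at 0.1% Grade 4 to 11.8 points (80.6 − 68.8) at 1%. The shortfall against 80% lies mainly near the 10% rate; at 5% it appears only when Grade 4 approaches 1%.

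Two limits apply. The model counts only treatment-related Grade 4 events, whereas Section 5.0's stage 1 clause omits that qualifier; if unrelated events count, acceptance is lower still. And the stated pair reproduces only with the more-than-1-of-6 boundary. Under the Interim Analysis boundary, with Section 5.0's final limit and no Grade 4, the 10% limit is slightly exceeded at 10.6%.

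**What to change.** First reconcile the stopping rules in Section 4.1 (General Design and Interim Analysis) and Section 5.0. Which rule should stand is not for this review to say. Then recompute the operating characteristics for the reconciled rule, including the at-most-10% statement.

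Then say in Section 5.0 what the probabilities cover. If the present Section 5.0 boundaries remain, this would do: *These probabilities are for the Grade ≥3 boundaries (at most 1 of 6, at most 3 of 20), assuming no Grade 4 toxicity; with the zero-Grade-4 condition included, the probability of acceptance is lower.* A short range over assumed Grade 4 rates could follow but is optional.

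The cost is one sentence and a brief recalculation once the sections agree. The labelling itself changes neither sample size nor analysis.
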